Prior studies have estimated that about half of the recent growth in health expenditures is attributable to advances in various forms of health technology, including new pharmaceutical products, surgical procedures, imaging modalities, and new biomarkers[29]. While almost all of these new technologies offer some potential to improve clinical outcomes, they also more often than not add to health expenditures. Within the context of unsustainable trends in health expenditures, a key policy question relates to whether the extent of improvement in outcomes associated with the use of a new technology is attained at a "reasonable" additional cost, compared to existing technology. Indeed, the value offered by new technologies is being subjected to increasing scrutiny by reimbursement authorities in many health systems worldwide. For example, in the United Kingdom, the National Health Service bases payment policy decisions for new technologies on recommendations from the National Institute for Health and Clinical Excellence (NICE), which in turn are substantially influenced by cost-effectiveness analysis yielding an estimated additional "cost per quality-adjusted life-year (QALY) gained" via use of the new technology. Currently, NICE usually considers technologies offering improved outcomes at a cost less than £20,000 to £30,000 per QALY gained (about \$33,000 - \$50,000) acceptable, though exceptions are common[30].

Therefore, we propose to collect cost information in both arms in this Phase III trial, and assess patients' health related quality of life, in order to evaluate the economical consequence of using the new technology proposed in this study and its impact on quality of life. We hypothesize that the new technology may be cost saving (cost less than the current standard of care) over the patient's entire treatment course, making it very attractive for adoption in treatment for lung cancer patients. Alternatively, we hypothesize that the new technology will increase quality-adjusted life-years for lung cancer patients (compared to the current standard of care) at a reasonable incremental cost, as defined by generally accepted cost-effectiveness thresholds.

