6.1.2 Dose Fractionation for Arm A

Patients on Arm A will receive 15 fractions of radiation. Patients will receive 4.0 Gy per fraction for 15 fractions (total dose = 60 Gy). All fields must be treated daily. Plan adaptation for treatment response is allowed and encouraged. (see Section 6.1.1)

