6.2.2 Dose Fractionation for Arm B

Patients on Arm B will receive 30-33 fractions of radiation at 2 Gy per fraction (total dose 60-66 Gy). There will be no field reductions, and all fields must be treated daily including the entire PTV treated daily.

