9.8 Cost-Effectiveness

Health care utilization data needed to assess costs will be obtained at the baseline visit (for the prior one year period) and at each follow-up visit (see Appendix II). Questions will be asked for the utilization of all the health care services (see Appendix VI). The health utilization data will be collected at each study site. They will be transferred to the data management center located at the Department of Epidemiology and Biostatistics, Texas A&M Health Science Center (TAMHSC). At TAMHSC, a designated staff member will be responsible for calling each health service provider and obtain the bills that are associated with each service reported in the CRF, with costs calculated using methods outlined below and stored in a designated computer for analysis purpose. Patients will be given a diary at the beginning of the study to aid in recording all health related visits and expenditures. Additionally, in order to assess the treatment related indirect costs and patient out of pocket costs, a form will be administered during the last week of treatment or at the first available follow up visit after completion of radiation treatment (see Appendix VII).

Hospitalizations: Inpatient admissions (hospitalizations for any reason) with dates of admission and discharge and name of hospital. Patient bills (UB-04s) also will be obtained for each hospitalization. Inpatient facility costs will be estimated by total billed charges adjusted by a facility-specific cost-to-charge ration from Medicare Cost Reports. We also will attempt to obtain billing records for inpatient physician services. For hospitalizations with physician billing records, impatient physician costs will be estimated by applying Medicare payment rates under the RBRVS-based Medicare Fee Schedule to billed procedures in the physician billing records. For hospitalizations where physician billing records are not available, inpatient physician costs will be estimated using a multivariate regression model from data that combines Medicare inpatient and physician bills. This is to

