10.0 Data Collection

Patient, treatment, HRQOL, and patient perspective costs data (Appendix VII) should be submitted to:

Department of Radiation Oncology
Clinical Research Office
The University of Texas Southwestern Medical Center
Attention: [name], Project Manager
[name]
[name]
[contact]

Economic data (patient bills, and other cost documents) will be collected by:

Department of Epidemiology and Biostatistics School of Rural Public Health Texas A&M Health Science Center, [name]

Attn: [name] [name] [name]

Patients will be identified only by initials (first middle last) and a unique study ID number assigned to each study participant; if there is no middle initial, a hyphen will be used (first-last). Last names with apostrophes will be identified by the first letter of the last name. Identifiable information will be released to Drs. [name] and [name] at Department of Epidemiology and Biostatistics, Texas A&M Health Science Center (TAMHSC) for obtaining the bills that are associated with each service reported in the case report forms.

Item	Due
Demographics	Within 2 weeks of study enrollment
Eligibility and Entry Characteristics, including baseline H&P and Zubrod PS	Within 2 weeks of study enrollment
Pathology Report	Within 2 weeks of study enrollment
Follow-up H&P data	At post XRT follow-up at 1, 3, 6, 9, and 12 months, then q 4 months year 2, then q6 months years 3-5; then annually
Tumor response evaluation	At post XRT follow-up at 3, 6, 9, and 12 months, then q 4 months year 2, then q6 months years 3-5; then annually
Adverse Event assessment	After each weekly treatment visit, then post XRT follow-up at 1, 3, 6, 9, and 12 months, then q 4 months year 2, then q6 months years 3-5; then annually
Healthcare Utilization/Cost Worksheet (Appendix VI),	Within 2 weeks of study enrollment, at the end of treatment, and at post treatment follow up at 1, 3, 6, 9, and 12 months, then q 4 months year 2, then q6 months years 3-5; then annually until death
FACT-L (Appendix VIII), EQ-5D (Appendix IX)	Within 2 weeks of study enrollment, at the end of treatment, and at post treatment follow up at 6 and 12 months,
Patient Perspective Cost Assessment (Appendix VII)	Upon radiation completion or first possible post treatment follow up (1 month). To be administered just once.

Data collection for QA

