	APPENDIX VII Patient Perspective Cost Assessment

We would like to ask you about your health coverage and the "out-of-pocket" costs you have had related to your cancer treatment.

	Do you have any coverage that helps pay for your medicines , when you are NOT in the hospital: (Check ALL that apply) Yes by Government (e.g., Medicare Part D, Tricare, etc.) Yes by private or employer-paid health insurance (supplemental) No coverage Don't Know
2.	Do you have any coverage that helps pay for home health or therapy , when you are NOT in the hospital (i.e. nursing, physiotherapy, respiratory therapy etc.): (Check ALL that apply) Yes by Government (Medicare, Medicaid, Tricare) Yes by private or employer-paid health insurance No coverage Don't Know

3. If you have Private/Employer-paid health insurance, please describe your coverage for each type of service: (For each service, check the box that best describes your level of coverage.)

TYPE OF	√ Don't Know	✓ Not Covered	✓ Partial	√ Full
SERVICE			Coverage	Coverage
Hospital supplemental charges (e.g. Private room, etc.)				
Prescription drugs (e.g. Antibiotics, pain medication, etc.)				
In home healthcare (e.g. home health nursing, physical therapist, respiratory therapy, etc.)				

Homemaking services (e.g. cleaning, cooking, etc.)		
Alternate Therapy (e.g. Homeopathy, Chinese medicine, over the counter drugs, etc.)		
Other (Specify)		

Proceed to Question 4

4. Please supply the following details regarding your "out-of-pocket" costs for trips to and from your radiation treatments and doctor visits **related to your cancer** *during the radiation treatment.*

Type of Visit	Number of trips during radiation treatment	ONE WAY OR origin and destination points	Method of transport (car, taxi, bus, train etc.)	Parking or Fare or Valet	Paid for by Insurance/ Government (circle one)
Cancer Clinic/ Radiation Facility		Miles		\$	□ None □ Partial □ Full
Hospital		Miles		\$	□ None □ Partial □ Full
Family Doctor		Miles		\$	□ None □ Partial □ Full
Other (Specify, i.e. 2 nd Hospital or 2 nd Doctor, ER)		Miles		\$	□ None □ Partial □ Full

- 5. For questions listed below indicate if you had cancer related costs, paid by yourself, private insurance or Medicare/Medicaid/Tricare *during the radiation treatment*. If you do not know the exact amount make your **best estimate**, rounded to the nearest dollar.
 - a) Copays (during the radiation treatment)

	☐ Yes (Check all that apply and fill in related estimate of dollar amount)						

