	 □ Doctor visits □ Emergency room visits □ Overnight hospitalization – indicate duration □ one or nights. □ Home nursing services □ Respiratory/ Physical/ Occupational Therapy services □ Medication changes □ Started oxygen treatment 							
8.		h time during rad related to your	iation treatment did you tal	ke off work to receive				
		'	No time off work □ Retired	days				
9.	Was this	time away from v	/ork: (Check ALL that a	oply)				
		pplicable (not worki off without pay	ng) 🗆 Vacation 🗅 Time	off with pay				

10.Did friends or fai treatment	mily take time away f	rom work in the	last 30 da	ys related to y	our
□ No time off v	vork	OR		days	
We would now like education:	to ask you a little k	oit about you, y	our work	and your	
11.Year of Birth					
12.Sex: □ Male	□ Female				
13.Marital Status:					
□ Married□ Widowed		-	(never marri Divorced	ed)	
14.How many other are only visiting)	people do you share):	e your home with	າ (do not ir	nclude people	who
□ Live alone (□ o □ 2 others □ More than 3 o		□ Myself and c□ 3 others	ne other		
15. Are these people	e you share your hon	ne with:			
□ Family	□ Friends □ Bot	h Family and Fr	iends		
16.City or Town wh	ere you live		_Zip code_		
17. How woul	d you rate your curre	nthealth?			
☐ Excellent	☐ Very good	☐ Goo	d	Fair	
□ Poor					
18.What do you do	for a living:				
☐ Full time work : \$	Specify	□Part time work	:: Specify		
☐ Retired	☐ Homemaker	☐ Unempl	oved	☐ Student	

	The patient A caregiver Both the patient and a caregiver
23.	Was this questionnaire completed by:
22. to	What treatments or services that are not currently available would you like see paid for through government or private insurance:
5:	□Not a burden at all □Only a slight burden □Somewhat of a burden □Significant burden, but manageable □Un manageable burden
	ow much of a financial burden are these out-of-pocket expenses listed in Q 4 &
	□Less than \$5,000 □\$5,000- \$9,999 □\$10,000- \$14,999 □\$15,000- \$19,999 □\$20,000-\$29,999 □\$30,000-\$39,999 □\$40,000-\$49,999 □\$50,000-\$59,999 □\$60,000-\$79,999 □More than \$80,000 □Don't Know
20.W	hat was your total family income before taxes in the last year. (include wages, salaries and self-employment earnings)
	 No schooling, some elementary school, or completed elementary school Some high school Completed high school Some university or community college Completed university or community college Post Graduate (MSc/MBA/PhD) or professional training (MD/LLB/DDS)

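### Appendix VII item 10 asks about caregivers' time off work in the last 30 days, a window longer than Arm A's course and shorter than Arm B's

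*Combined protocol and SAP*

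**What the plan says.** Section 9.8 gives the form its purpose, "in order to assess the treatment related indirect costs and patient out of pocket costs", and its timing: "a form will be administered during the last week of treatment or at the first available follow up visit after completion of radiation treatment". Section 10.0 states the timing as "Upon radiation completion or first possible post treatment follow up (1 month). To be administered just once". Appendix II marks the form for the last week of radiation and for the 1-month visit, with a footnote allowing completion of treatment or first follow-up.

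Most cost items on the form refer to the radiation period. Item 4 has a column headed "Number of trips during radiation treatment". The opening of item 5 (copays, drugs, home care, family care, lodging and so on) and item 8 (the patient's own time off work) use the same reference period. Item 10 asks instead how much time friends or family took away from work over the last 30 days because of the treatment. The Appendix VI utilization worksheet does not ask about caregiver time.

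The courses differ in length. For Arm A, section 6.1.2 says: "Patients will receive 4.0 Gy per fraction for 15 fractions (total dose = 60 Gy". For Arm B, section 6.2.2 says: "Patients on Arm B will receive 30-33 fractions of radiation at 2 Gy per fraction (total dose 60-66 Gy".

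**The concern.** A recall window of fixed length is a fair measure of time lost to treatment only if it holds the whole course in both arms, or the same share of each. Here it is longer than one arm's course and shorter than the other's. The undercount is therefore differential by arm, and a larger sample would not remove it. Its size also changes with the date on which the form is completed, and two dates about a month apart are permitted.

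What is at stake is the description of treatment-related indirect cost, which is the task section 9.8 gives this form. No other form records caregivers' time off work, so what item 10 misses cannot be recovered from another source. The direction is predictable: any saving in caregiver time from the shorter course would look smaller than it is.

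**Working it through.** **Inputs.** Arm A has 15 fractions (section 6.1.2) and Arm B has 30-33 (section 6.2.2). The recall window is 30 days ending on the form date (Appendix VII item 10). Permitted form dates run from the last week of radiation to the first follow-up, nominally 1 month (sections 9.8 and 10.0, Appendix II). Assumptions: weekday treatment, five fractions a week, no breaks.

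**Check against the plan's own figures.** Weeks = fractions / 5.
- 15 / 5 = 3.0
- 30 / 5 = 6.0
- 33 / 5 = 6.6

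Section 1.2 describes a retrospective comparison in which 45 Gy at 3 Gy (15 fractions) took 3 weeks and 60-66 Gy at 2 Gy (30-33 fractions) took 6 to 6.5 weeks. The assumption reproduces these closely.

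**Calendar length over all weekday starts.** 15 fractions span 19-21 days, 30 fractions span 40-42 days, and 33 fractions span 45-47 days.

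**Form on the last treatment day.** Coverage = min(30, course length) / course length.
- Arm A: 100%, since 30 exceeds 21. The window also takes in 30 - 21 = 9 to 30 - 19 = 11 days before treatment began.
- Arm B, 30 fractions: 30/42 = 71% to 30/40 = 75%.
- Arm B, 33 fractions: 30/47 = 64% to 30/45 = 67%.

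Counted in fractions, the window holds 21 or 22 Arm B treatment days, depending on the weekday of the last fraction: 21/30 = 70% to 22/30 = 73%, or 21/33 = 64% to 22/33 = 67%.

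**Form on other dates (share of course days covered).**

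| Form date relative to last fraction | Arm A | Arm B |
|---|---|---|
| 4 days before | 79-81% | 64-75% |
| Same day | 100% | 64-75% |
| 14 days after | 76-84% | 34-40% |
| 28 days after | 10-11% | 4-5% |
| 30 or more days after | 0% | 0% |

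For example, at 14 days 30 - 14 = 16 course days remain in the window: 16/21 to 16/19 in Arm A, 16/47 to 16/40 in Arm B. In the first row, the part of Arm A's course not covered had not yet been delivered.

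**Illustration of the between-arm effect.** Suppose caregivers lose the same time per fraction in both arms (an assumption; the documents give no figure). The true difference is 30 - 15 = 15 to 33 - 15 = 18 fractions' worth. A form on the last treatment day records 21 - 15 = 6 or 22 - 15 = 7. The understatement is:
- 30 fractions: 1 - 7/15 = 53% to 1 - 6/15 = 60%
- 33 fractions: 1 - 7/18 = 61% to 1 - 6/18 = 67%

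**After the change.** With item 10 referring to the radiation treatment period, coverage is 100% in both arms at completion or at 1 month. A form completed before the last fraction would miss only the remaining days.

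**The case against.** The strongest reply is that this is one item of 30 and that no planned analysis uses it. That largely stands. Section 11.5.3 estimates cost accumulated within 2 years by inverse-probability weighting, and the costing rules in section 9.8 value hospital stays, radiation treatment, emergency visits, clinic visits, drugs and home care. Neither section assigns a value to caregiver time. A reader might infer that the whole form is truncated, or that the primary cost result is biased. The documents support neither: items 4, 5 and 8 are tied to the radiation period, and item 10 is not named in the cost estimate. Nor does the hypothesis in section 1.3, that the new treatment may "cost less than the current standard of care) over the patient's entire treatment course", mention caregiver time, so item 10 cannot be said to threaten it. No passage ranks caregiver time above travel, lodging or other family costs.

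On timing, a reader might infer that sites choose freely between two equal dates. The fairer reading is that the form belongs at the end of treatment and the first follow-up is a catch-up, since section 9.8 names the last week first and section 10.0 speaks of the first possible visit. Near-zero coverage therefore describes the catch-up case. It remains permitted, and the arms already differ when the form is completed on the last treatment day.

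A short fixed window is also a defensible choice when a patient reports on other people's absences, and item 6 refers to the past month too. That is a reason for choosing such a window, but it does not make the answers comparable when one course fits inside the window and the other does not.

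Finally, the per-fraction model is crude. Arm A's window includes 9-11 days before treatment, when visits could add caregiver time, and section 7.0 allows concurrent chemotherapy in Arm B only, which may cost caregivers time unrelated to fractions. The percentage should be read as an order of magnitude.

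**Conclusion.** The inconsistency is real and its scope is narrow. Item 10 does not measure caregiver time over the course on the same basis in the two arms. On the last treatment day it covers 100% of Arm A's course and about 64-75% of Arm B's; at 28 days about 10% and 4-5%; at 30 days or more, none of either. These figures rest on five fractions a week without breaks, and the documents give no window for the 1-month visit.

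The 53-67% understatement of the between-arm difference also needs equal caregiver time per fraction and a form completed on the last treatment day, so it is illustrative and not an estimate of what the trial will see. The consequence is limited to the indirect-cost description. The primary endpoint is not involved, and the documents do not show item 10 entering the cost-effectiveness ratio. This is a minor correction that is worth making because it costs almost nothing.

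**What to change.** Reword item 10 so that it asks about time off during the patient's radiation treatment, the reference period already used in items 4, 5 and 8. Record the date on which each form is completed, so that forms filled in before the last fraction, or well after it, can be identified. The existing timing can stay.

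For forms already collected with the 30-day wording, do not compare item 10 between arms as total caregiver time for the course. If it is reported, describe it as time off in the 30 days before the form and give the timing of completion by arm.

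The cost is one phrase and one date field on Appendix VII. No visit, form or treatment rule changes.

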11.0 Statistical Considerations

11.1 Study Endpoints

11.1.1 Primary Endpoint: Overall survival (Failure: death from any cause)

11.1.2 Secondary endpoints:

11.1.2.1 Quality of Life (QOL) as measured by the Functional Assessment of Cancer Therapy Lung subscale (FACT-L)

11.1.2.2 Cost effectiveness analysis

11.1.2.3 Progression-free survival (Failure: occurrence of local or regional progression, distant metastases, or death from any cause)

11.1.2.4 Toxicity: Grade 3-5 adverse events as graded by CTCAE v 4.0

11.2 Sample Size Determination

The sample size calculation is based on the primary endpoint, overall survival at 1 year, and the assumption that patients are randomized until the end of accrual. The sample size is calculated with the 2-sided significance level of 0.05 and 80% statistical power using a 2-sample log rank test. We assume that the overall survival function follows an exponential distribution for each arm. Accrual to the study is assumed to be uniformly distributed. The null hypothesis is that the there are no difference in 1-year survival rates between two arms. We assume that the patients will be accrued for 2 years with a 1-year follow-up. We hypothesize that the patients randomly assigned to the control arm and experimental arm have a 1-year survival rate of 45% (hazard rate [λc]) of 0.799) and 60% (hazard rate [λe]) of 0.511), respectively, which is translated to the hazard ratio of $\lambda e/\lambda c = 0.640$. One interim analysis and a final analysis are planned for early stopping for efficacy. The efficacy testing is based on the Lan-DeMets spending function, which resembles the O'Brien-Fleming boundary. The total sample size of 226 patients (113 in the control arm and 113 in the experimental arm) will be accrued to achieve the desired 80% statistical power and 2-sided significance level of 0.05. Guarding against ineligibility or lack-ofdata rate of up to 5%, the final targeted accrual for this study will be 238 patients (119 per arm). Sample size was estimated using the sample size software EaST version 5.

11.3 Patient Accrual

Patient accrual is projected to be 4 patients per month. This trial should complete the accrual phase in 60 months. If the monthly accrual is less than 2 cases per month, the study will be reevaluated with respect to feasibility.

11.4 Randomization Scheme

Patients will be allocated to the treatment using a randomized permuted block within strata to balance for patient factors other than institution. The stratifying variables are Zubrod performance status (2 vs. > 2) and stage (II vs. III).

11.5 Analysis Plans

All eligible patients who are randomized to the study will be included in the comparison of treatment arms, regardless of treatment compliance (intent-to-treat analysis).

